#### **Hypothesis Testing for Metabolic Cost:**

We tested the hypothesis that exposure to repetitive, acute intermittent hypoxia decreased net metabolic power using a mixed model ANOVA at a 0.05 significance level; the between subject's factors is intervention (AIH vs SHAM), and the within subjects' factors is time (initial, early change, plateau), with net metabolic power as dependent variable. A multiple linear regression was implemented to determine the spatiotemporal variables associated with capacity to reduce asymmetry and net metabolic power for the following independent variables:  $MEP_{max}$ , recruitment curve slope, step length, step time, stance duration and baseline metabolic power. Variance inflations factors were calculated to avoid multicollinearity with the Akaike information criterion model utilized for model selection.

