### APPROACH:

**Methodology:** We implemented a placebo controlled, two group study design that characterized how changes in corticospinal excitability are associated with motor adaptation and walking energetics in 26 persons following repetitive exposure to AIH. Each intervention involved 5 consecutive treatment visits. For each treatment visit, participants received an exposure [15, 1.5 min episodes at 9% O2 (AIH) or 21% O2 (SHAM) at 1 min intervals]. Split belt adaptation assessments and metabolic cost quantification protocols were implemented at the end of each intervention. Delivery of intermittent gas mixtures was accomplished using air generators [HYP123, HypoxicO] attached to a non-rebreathing face mask. In order to ensure subject safety during interventions, we monitored oxygen saturation (SpO2), heart rate, respiratory rate and blood pressure [Root 7, Masimo] at 1 second intervals.

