**Sensorimotor Adaptation:** We characterized motor adaptation by quantifying changes in step asymmetry in response to split belt treadmill speed perturbations, before and after repetitive AIH exposure. Step asymmetry was quantified as the ratio of normalized difference in step lengths of each leg. Temporal asymmetry was computed from the time series of joint angles as the lag time at peak cross-correlation of limb angle trajectories. The first 5-10 strides of the 'adaptation' and 'de-adaptation' epochs were used to quantify speed perturbation induced effects. Motor adaptation was evaluated relative to the baseline epoch by comparing step asymmetries during the first and last 10 steps of the 'adaptation' and 'de-adaptation epochs'. A greater difference indicates greater motor adaptation. Improvement of interlimb coordination was estimated based on decreases of asymmetry in both spatial and temporal step parameters. We compared changes in step asymmetry and interlimb coordination between AIH and SHAM interventions.

**Net Metabolic Power:** We quantified the metabolic costs during treadmill gait before and after AIH during the final 2 minutes of the motor adaptation epochs. We identified spatiotemporal gait parameters that affect the capacity to minimize the metabolic cost in participants with iSCI. We measured the net metabolic power during treadmill walking as the rate of metabolic energy consumption. Participants wore a nose clip and breathed in and out of a mouthpiece to measure the rates of O2 consumption VO2 and CO2 production VC02 (liter/min) using expired gas analysis [ParvoMedics, TrueMax2400]. The measured rates (liter/min) of VO2 and VC02, which we then converted to metabolic power (J/s) using the Brockway equation as the outcome measure representing the rate of metabolic energy consumption. Metabolic power was normalized to the subject's body weight (J · s · kg). To calculate net metabolic power, we subtracted baseline resting metabolic power while quiet standing.

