#### **Hypothesis Testing for Motor Adaptation:**

Spatiotemporal asymmetry parameters were calculated in each epoch (adaptation, second adaptation) in 3 periods: initial (mean of first 5 strides), early (mean of strides 6-20), and the late (mean of last 30 strides). Differences from BL to adaptation was compared between and within interventions using a mixed model ANOVA at a 0.05 significance level; the between-subjects factor is intervention (AIH vs. SHAM), and the within-subjects factor is time (initial, early change, late), with spatiotemporal parameters (e.g., step length asymmetry, step time asymmetry) as the dependent variables. Analysis of covariance (ANCOVA) was used if PRE measures are significantly different between interventions. If sphericity was violated, we used the Huynh-Feldt corrected p value. Post hoc comparisons used the Tukey-Kramer correction for multiple comparisons.

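### The net metabolic power ANOVA uses a time factor that does not match the stated measurement window, and it names no PRE-to-POST contrast of AIH with SHAM

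*Combined protocol and SAP*

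**What the plan says.** Four statements in the combined protocol and SAP bear on this point.

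- **Measurement** (Approach, Net Metabolic Power): "We quantified the metabolic costs during treadmill gait before and after AIH during the final 2 minutes of the motor adaptation epochs". Net power is then obtained by subtraction: "we subtracted baseline resting metabolic power while quiet standing".
- **Test** (Hypothesis Testing for Metabolic Cost): the hypothesis is that repetitive AIH reduced net metabolic power. It is tested at 0.05 in a mixed model ANOVA with intervention (AIH vs SHAM) between subjects; for the within-subject part, the "factors is time (initial, early change, plateau), with net metabolic power as dependent variable".
- **Regression** (same section): a separate multiple regression has among its predictors "recruitment curve slope, step length, step time, stance duration and baseline metabolic power". Whether that baseline is the resting value or the PRE walking value is not stated.
- **Timing and design** (Approach, Methodology): "Split belt adaptation assessments and metabolic cost quantification protocols were implemented at the end of each intervention". The design is introduced thus: "We implemented a placebo controlled, two group study design". The available text does not say how participants were allocated.

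**The concern.** There are two gaps between what was measured and what was tested.

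The first is the window. A value taken in the final 2 minutes of an epoch can be the plateau level at most. The available text defines no gas-collection window for the initial or early change levels.

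The second is the contrast. The hypothesis concerns a reduction, and the protocol says values were taken before and after. The ANOVA names only intervention and the three-level time factor. Its intervention main effect compares levels between arms. Its intervention x time term compares the shape of the course over the three levels. Neither is the AIH-versus-SHAM difference in PRE-to-POST change, and the plan does not say which term answers the hypothesis or which session's data enter.

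At stake are interpretation and precision. If allocation was not random, freedom from bias is also at stake.

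**Working it through.** The plan gives no power calculation or variance for this outcome, so there is no figure to reproduce. The check is first textual, then an illustration.

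**1. Can other text supply the missing pieces?**

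- *Net* removes quiet-standing power, not PRE walking power.
- *Early change* is one level of the time factor, not a PRE-to-POST change score.
- *Baseline metabolic power* enters only the regression.
- The nearest definition of the levels is for asymmetry, under Motor Adaptation: "calculated in each epoch (adaptation, second adaptation) in 3 periods: initial (mean of first 5 strides), early (mean of strides 6-20", with a late period of the last 30 strides. These are stride counts, and the third level is not called plateau.
- The plural *epochs* could give more than one final-2-minute value, but those would be epochs, not the three levels.
- PRE/POST appears as a factor only under Corticospinal Excitability. ANCOVA on PRE, if PRE differs significantly, appears only under Motor Adaptation.

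**2. Inputs for the illustration.** The Methodology paragraph gives 26 participants. Assumed: 13 per arm, two-sided 0.05, equal SDs, POST data in the stated ANOVA. Power comes from the noncentral t with noncentrality d / (f x sqrt(2/13)), where sqrt(2/13) = 0.392, d is the difference in SD units, and f is the SD of the analysed quantity relative to a single value.

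**3. Main effect of the stated ANOVA** (mean of three levels, correlation w between levels, f = sqrt((1+2w)/3), 24 df):

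| d | w = 0.5 (f = 0.816) | w = 0.7 (f = 0.894) | w = 0.9 (f = 0.966) |
|---|---|---|---|
| 0.8, AIH effect equal at all levels | 0.669 | 0.590 | 0.527 |
| 0.5, no AIH effect, lasting arm difference | 0.323 | 0.278 | 0.245 |
| 0.3, no AIH effect, lasting arm difference | 0.147 | 0.130 | 0.118 |

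The last two rows are rejection rates to set against 0.05. They apply only to a systematic difference between arms that carries over in full from PRE to POST.

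**4. Intervention x time term** (2 and 48 df). The noncentrality is 6.5 x S / (1-w), where 6.5 = 13 x 13 / 26 and S is the sum of squared deviations of the three level-specific effects from their mean.

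- Equal effect of 0.8 SD at all levels: S = 0, so rejection stays at 0.05. Simulation gave 0.0495, 0.0512 and 0.0488.
- Effect of 0.8 SD at plateau only: S = 0.427; power 0.52, 0.76, 0.997 at w = 0.5, 0.7, 0.9.
- Gradual 0 / 0.4 / 0.8 SD: S = 0.32; power 0.41, 0.62, 0.98.

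**5. Options for the final-2-minute value** (d = 0.8 at POST, no PRE imbalance, one value per session, PRE-POST correlation rho):

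| Analysis | f | rho 0.3 | 0.5 | 0.7 | 0.8 |
|---|---|---|---|---|---|
| POST only, 24 df | 1 | 0.499 | 0.499 | 0.499 | 0.499 |
| Change score, 24 df | sqrt(2(1-rho)) | 0.380 | 0.499 | 0.715 | 0.871 |
| ANCOVA on PRE, 23 df | sqrt(1-rho²) | 0.535 | 0.616 | 0.781 | 0.902 |

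With PRE simulated as a random covariate, ANCOVA gives 0.519, 0.593, 0.760 and 0.883. A 16/10 split shows the same pattern (POST only 0.478; ANCOVA 0.513 to 0.886). These figures compare options; they are not the power of this study.

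**6. ANCOVA versus change score.** With a PRE difference between arms the two estimates differ by (1-rho) x that difference. For 0.5 SD this is 0.35, 0.25, 0.15 and 0.10 SD at rho = 0.3, 0.5, 0.7 and 0.8.

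**The case against.** The strongest reply is that this is terse drafting rather than a wrong analysis, and that a placebo-controlled comparison of POST values needs no PRE term. Much of that stands, and it rules out several stronger readings.

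- *The analysis is biased.* Not shown. Under random allocation the POST main effect is a valid test. Silence on allocation in an incomplete text does not establish that allocation was not random. The rates of 0.118 to 0.323 do not describe chance imbalance: conditional on an observed chance PRE difference of 0.3 or 0.5 SD, simulation (w = 0.7) gave rejection between 0.005 and 0.067, and averaged over random allocation the rate is 0.05.
- *The interaction has no power.* True only for an effect equal at all three levels. It can show an effect that builds up over the epoch, although as a POST contrast.
- *PRE data are ignored altogether.* Only the ANOVA omits them. The regression's baseline term may be a PRE value.
- *Only this outcome lacks the contrast.* Not so. The excitability model names no SHAM factor, and the motor adaptation model has a similar structure with only a conditional ANCOVA. For asymmetry, the Approach section does state the aim: "We compared changes in step asymmetry and interlimb coordination between AIH and SHAM interventions".
- *No early gas data exist.* Not shown. They may have been recorded, with the levels simply left undefined.

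What the reply does not remove is that the stated levels do not fit the stated window, and that the ANOVA makes no use of a PRE value the protocol says was taken.

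**Conclusion.** The point holds, limited to the text available for review, and should be fixed. The mismatch of window and time levels, and the absence of any PRE term from the ANOVA, can be read directly, and confidence in them is high. The consequence depends on a fact the available text does not give. With random allocation the cost is precision: for a single final-window value, 0.499 unadjusted against 0.535 to 0.902 adjusted, under the assumptions above. Without it, the main effect cannot separate an AIH effect from a lasting difference between arms. The documents do not settle which case applies, so a finding of actual bias would go too far.

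**What to change.** 1. Reconcile the final-2-minute window with the three time levels, and define a gas window for each level that is kept.
2. Reconcile the timing: Methodology places metabolic testing at the end of each intervention, while Net Metabolic Power says before and after. Check that PRE values exist in both arms.
3. Where they do, report AIH versus SHAM on POST net metabolic power over the final 2 minutes, adjusted by ANCOVA for the PRE value from the same epoch and window. The analysis is reported as already done, so label this post hoc.
4. If earlier gas windows were recorded, keep the three-level time course as a secondary analysis, also adjusted for PRE.
5. State whether allocation was random. If it was not, also report the change-score contrast, since the two can then estimate different quantities.
6. If PRE is missing in an arm, report a POST difference between arms and do not call it a decrease.
7. Say whether the regression's baseline term is resting or PRE power.

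The cost is revised wording, a data check and one re-run model. There is a trade-off: if AIH acts equally in three real windows, their unadjusted mean (0.527 to 0.669) can have more power than final-window ANCOVA at low PRE-POST correlation (0.535 at rho = 0.3).

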**Transcranial Magnetic Stimulation:** TMS was delivered via a custom-built batwing coil for leg stimulation connected to a DUOMAG unit [Deyemed]. Single pulse TMS with monophasic current waveform was applied to the contralateral motor cortex of the more impaired target TA muscle. Coil position and head position were digitally tracked to ensure similar coil placement in repeated measurements using a Visor 2LT optical system [ANT Neuro]. The hot spot was defined as the region where largest and most consistent MEPs are evoked using a stimulation intensity of 1.2 x resting motor threshold (RMT) intensity. RMT was defined as the stimulator output intensity that elicits MEPs with peak-to-peak amplitudes greater than 50  $\mu$ V in four out of eight trials in the relaxed muscle. MEPs from the tibialis anterior were obtained during rest and at static contraction of up to 20% MVC. Real-time visual feedback about EMG contraction level was provided. The slope of the recruitment curve reflects gain in MEP amplitude with increasing stimulus intensity, providing an indication of gain modulation. TMS intensity was increased from below motor threshold at stimulator intensity intervals representing 90% to 120% of RMT. 20 randomized stimuli were given per stimulation intensity, and the MEPs were ensemble averaged for analyses. The mean MEP response was plotted against the corresponding stimulation intensity (% of RMT) to produce a stimulus-response recruitment curve. We compared recruitment curve parameters (MEPmax, slope) before and after AIH.

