### **STATISTICAL ANALYSES:**

#### **Hypothesis Testing for Corticospinal Excitability:**

We hypothesized that exposure to repetitive, acute intermittent hypoxia enhances CST excitability to the TA (i.e., increase  $MEP_{max}$  and recruitment curve slope) after repetitive AIH. TMS testing was completed within this time, as we expected this facilitation to persist for up to 1 hour post-AIH based on prior research in our lab. Data was evaluated for normality using the Kolmogorov-Smirnov test. If data satisfied the normality test, a repeated measures analyses of variance was used to determine if each excitability parameter differed across PRE and POST conditions. Sphericity was assessed using the Mauchly test. If sphericity was violated, we used the Huynh-Feldt corrected p value. Post hoc comparisons were used in the Tukey-Kramer correction for multiple comparisons.

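### AIC screening of six predictors in at most 26 people will often select noise, and if both arms are pooled the lack of an intervention term can add an arm-driven excitability association

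*Combined protocol and SAP*

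**What the plan says.** The section Hypothesis Testing for Metabolic Cost first sets out a mixed model ANOVA with intervention (AIH vs SHAM) as a factor, to test whether "exposure to repetitive, acute intermittent hypoxia decreased net metabolic power". It then adds a second analysis: "A multiple linear regression was implemented to determine the spatiotemporal variables associated with capacity to reduce asymmetry and net metabolic power". The candidates are MEPmax and "recruitment curve slope, step length, step time, stance duration and baseline metabolic power", six in all. On selection it says: "Variance inflations factors were calculated to avoid multicollinearity with the Akaike information criterion model utilized for model selection".

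For this regression the available text does not give:

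- which participants enter it;
- whether MEPmax and slope are PRE, POST or change values;
- how each outcome is computed;
- an intervention term;
- a cut-off for variance inflation;
- a small-sample correction, a validation step or an exploratory label.

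The Methodology paragraph gives 26 persons in a placebo controlled, two group design and frames the study around changes in excitability. The excitability section hypothesises that "exposure to repetitive, acute intermittent hypoxia enhances CST excitability to the TA", covering MEPmax "and recruitment curve slope) after repetitive AIH". Its test is to "determine if each excitability parameter differed across PRE and POST conditions". The Transcranial Magnetic Stimulation paragraph compares MEPmax and "slope) before and after AIH". Neither place describes MEPs in SHAM.

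**The concern.** AIC with six candidates and very few people is a permissive filter. It tends to keep something even when nothing is related to the outcome, and the model it keeps can fit the data well. Nothing in the plan tells a reader to treat the retained variables as provisional, so they could be reported as determinants of a better gait or a lower walking cost when they are selection noise.

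The missing intervention term raises a second question. The plan expects AIH to raise excitability and to lower metabolic power. If both arms are in one regression without a term for arm, those two effects can produce an association between excitability and outcome even when the two are unrelated among people given the same exposure. That would be read as a link in individuals. Checking variance inflation does not detect this, because it concerns collinearity among the predictors.

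**Working it through.** The plan gives no error rate or power figure for this regression, so there is none to reproduce.

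**Inputs from the document.** 26 people in two groups; six candidates; AIC selection.

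**Assumptions.** 13 per arm; normal errors; all-subsets search over the 64 possible models; no variance inflation screening; between-arm shifts d of 0.5, 0.8, 1.0 and 1.5 SD. The document gives no effect sizes.

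**1. Room for selection.** Residual degrees of freedom in the full model are 26 − 7 = 19, or 13 − 7 = 6 for AIH only. The expected R² from pure noise is 6/(n − 1): 6/25 = 0.24 and 6/12 = 0.50.

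**2. One noise variable.** AIC adds a term to an empty model when F > (n − 2)(e^(2/n) − 1).
- n = 26: 24 × 0.0800 = 1.92, which noise exceeds with probability 0.179.
- n = 13: 11 × 0.1663 = 1.83, probability 0.203.

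**3. Six noise variables.** Treating the six as separate chances gives 1 − 0.821⁶ = 0.69 and 1 − 0.797⁶ = 0.74. Simulation of the actual search (20,000 runs) gives the following.

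| n | AIC keeps at least one | AICc keeps at least one | Median R² of AIC-selected models |
|---|---|---|---|
| 26 | 71% | about 57% | 0.20 |
| 13 | 80% | about 48% | 0.47 |

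These rates are per outcome, and the plan names two outcomes.

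**4. Effect of variance inflation screening.** As an illustration, assume a correlation of 0.9 between step time and stance duration, 0.6 between step length and each of them, and a cut-off of 5. The AIC rates fall from 71% to 63% at n = 26 and from 80% to 72% at n = 13.

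**5. Arm-driven association, if it can arise.** Suppose AIH shifts an excitability measure and the outcome by d SD each, with no link inside either arm. With equal arms, the pooled correlation has size (d²/4)/(1 + d²/4). AIC retention of MEPmax or slope was simulated with both shifted and a within-arm correlation of 0.5 between them.

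| d (SD) | Pooled correlation | Kept, no intervention term | Kept, intervention forced in | Kept, no intervention term, three gait variables also shifted |
|---|---|---|---|---|
| 0.5 | 0.06 | 38% | 38-40% | 38% |
| 0.8 | 0.14 | 47% | 38-40% | 43% |
| 1.0 | 0.20 | 57% | 38-40% | 48% |
| 1.5 | 0.36 | 86% | 38-40% | 58% |

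Forcing intervention in returns retention to its noise level but does not reduce that level. With pure noise and intervention forced in, AIC still keeps at least one of the six in about 73% of runs, and AICc in about 54%.

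**6. Cost of the intervention term.** Residual degrees of freedom in the full model go from 19 to 18. Variance inflation between intervention and one shifted predictor is 1 + d²/4 = 1.06/1.16/1.25/1.56.

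**The case against.** The strongest reply is that this is a secondary, variable-identifying regression with no stated hypothesis test, and that the arm problem may not exist. Much of that stands. A reader might infer from the two-group design that the arms were pooled and the excitability result is confounded. The document does not support that reading. It names no population, describes MEPs only around AIH, and gives no MEP timepoint. With PRE values, or with AIH data alone, the artefact cannot arise. Even when it can, the excess is nil at 0.5 SD and smaller at larger shifts if gait also changes. Whether a within-arm or an across-arm association is wanted is also for the investigators to decide.

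A reader might also want false-positive rates at p < 0.05. The 0.05 level is stated for ANOVAs, not for this regression, so such rates would assume a reporting rule the plan does not contain. Retention by AIC is the rule it does state, and the figures here use it.

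The rates are somewhat high because the planned variance inflation screening was not modelled. The illustration lowers them by about 8 points and leaves the conclusion unchanged.

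Finally, the stated purpose is to identify gait variables, so a remedy that removed them would replace the analysis. That is right, and they should stay. None of these replies answers the over-selection itself, which is present whichever population was used.

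**Conclusion.** The concern holds, with noise selection as the main point. Under independent noise predictors, AIC keeps at least one of six in about 71% of analyses in 26 people and about 80% in 13, or somewhat fewer after collinear gait variables are dropped. At n = 13 the selected noise models have a median R² of 0.47, which could look persuasive.

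The missing intervention term matters only if arms are pooled, SHAM MEPs exist, and POST or change values are used. Under those conditions the excess is negligible at 0.5 SD, modest at 0.8 to 1.0 SD, and large at 1.5 SD unless gait also shifts. The 13/13 split and the shifts are assumptions.

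A reader might go further and doubt the trial's comparison of AIH with SHAM. That does not follow, because the ANOVAs for motor adaptation and metabolic power include intervention as a factor and do not depend on this regression. Parts of the document were not available for review, and they could settle the population or the timepoint.

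**What to change.** 1. State the population, the formula for each outcome, and what baseline metabolic power means. The Net Metabolic Power paragraph uses similar wording for resting power while standing, which is not PRE net walking power.
2. If both arms are used, force intervention into every candidate model, outside the selection step. If an across-arm association is wanted instead, say that it includes the AIH effect.
3. Use PRE-to-POST change in MEPmax and slope, which matches the aim in the Methodology paragraph.
4. Replace AIC with AICc, label the selected model exploratory, report bootstrap selection frequencies, and give no confirmatory reading to any post-selection p-value. AICc reduces noise retention to about 57% at n = 26 and 48% at n = 13. It does not remove it, so the label is still needed.
5. Keep the gait variables as candidates. A model with a single excitability measure may be added as a supplement. If the data have been seen, as the past tense suggests, describe it as chosen post hoc. State its power: about 66-68% for a within-arm correlation of 0.5 in 26 people (model with change in MEPmax, three gait variables, PRE power and intervention), and about 40% in 13 (change in MEPmax and PRE outcome only).

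The cost is revised wording, a re-analysis of existing data (including SHAM MEPs if arms are pooled), one residual degree of freedom (19 to 18), variance inflation of about 1.06 to 1.56, fewer retained variables and weaker claims from this secondary model.

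### If belt speeds differed between participants, the metabolic-power regression could report treadmill speed as an effect of step length or step time

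*Combined protocol and SAP*

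**What the plan says.** Under Statistical Analyses, Hypothesis Testing for Metabolic Cost, a multiple linear regression looks for "spatiotemporal variables associated with capacity to reduce asymmetry and net metabolic power". There are six regressors: MEPmax, and then "recruitment curve slope, step length, step time, stance duration and baseline metabolic power". Neither belt speed nor walking speed is among them. On collinearity and selection the section says: "Variance inflations factors were calculated to avoid multicollinearity with the Akaike information criterion model utilized for model selection". It gives no VIF cut-off and no rule for which variable to drop.

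Under Approach, Net Metabolic Power, the outcome is a rate: "We measured the net metabolic power during treadmill walking as the rate of metabolic energy consumption". It is scaled per kilogram, net of quiet standing, and taken over the last two minutes of the adaptation epochs, which are split-belt epochs. The same section states the interpretive aim: "We identified spatiotemporal gait parameters that affect the capacity to minimize the metabolic cost in participants with iSCI". It attaches the word baseline to the quiet-standing value; the regression section does not say whether its baseline power is that value or PRE walking power.

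The available text does not give the belt speeds or say whether they were common or individual. It does not define the regression outcome as a level or a change, or the gait regressors as raw values, changes or asymmetries.

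**The concern.** Step length and step time on a treadmill are tied together by belt speed. If some participants walked on faster belts, the two variables jointly carry that information. Metabolic power per second can be expected to rise with speed, and subtracting standing power does not remove this. A model with the gait pair but no speed term could then name step length or step time as related to metabolic power when the participants differed only in belt speed. The study's aim is to name gait parameters that affect metabolic cost, so this would be a wrong answer to one of its stated questions.

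**Working it through.** **Inputs from the document.** At most 26 participants ("in 26 persons following repetitive exposure to AIH"); six regressors; outcome in J/s/kg. The plan states no R², VIF or power for this regression, so there is no figure to reproduce.

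**Assumed inputs.** Mean speed 0.6 m/s; between-person coefficient of variation (CV) 15–35%; belt ratio 2:1 where belts are split; power depends on speed only, with no gait effect at a given speed. Model A: net power = 1 + 3v, 15% scatter, CV 15–30%. Model B: net power = 1 + 4v, residual SD 0.5, CV 15–35%. Each uses n = 26. The ranges for A cover variants of the inputs that had to be filled in.

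**Step 1: geometry.** Let x be the landing position of each foot, v its belt speed and t the step time during which that belt carries the stance foot back (s slow, f fast).
- Fast step length = x_f − (x_s − v_s·t_s)
- Slow step length = x_s − (x_f − v_f·t_f)
- Sum = v_s·t_s + v_f·t_f; the landing positions cancel.
- Mean step length / mean step time = (v_s·t_s + v_f·t_f)/(t_s + t_f), the time-weighted mean belt speed.

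At belts of 0.4 and 0.8 m/s with 45–55% of the time on the fast belt, the ratio runs from 0.8×0.45 + 0.4×0.55 = 0.58 to 0.8×0.55 + 0.4×0.45 = 0.62. For tied belts it equals belt speed exactly.

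**Step 2: how well the pair recovers speed (model B).** R² of speed on step length and step time: 0.985, 0.969 and 0.948 at CV 15, 25 and 35% (tied belts). With split belts at CV 25% it is 0.957 with both legs averaged and 0.827 with one leg.

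**Step 3: false gait findings.**

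| Outcome and baseline regressor | Measure | As planned | With speed in the model |
|---|---|---|---|
| Level, resting baseline (A) | AIC keeps step length | 79–97% | 22–25% |
| Level, resting baseline, tied, CV 15/25/35% (B) | gait terms jointly p<0.05 | 68/97/100% | about 4% |
| Level, resting baseline, split, CV 25% (B) | same | 97% both legs, 92% one leg | 3%, 5% |
| Level, walking baseline sharing the person's own scatter (A) | AIC keeps step length | 20–36% | 22–26% |
| Level, walking baseline with independent scatter, CV 25% (B) | jointly p<0.05 | 69% | 4% |
| PRE–POST reduction, matched speed (A) | AIC keeps step length | 20–38% | 22–26% |
| Reduction unrelated to speed, CV 25% (B) | jointly p<0.05 | 3% | 4% |
| Reduction proportional to power, CV 25% (B) | jointly p<0.05 | 14% | 5% |

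For A, speed is forced in; for B, it replaces step length. If the regressor is step-length asymmetry and the outcome a level, AIC keeps it in 20–23% of runs, which is the chance rate.

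The two walking-baseline rows differ for a reason. In B, speed contributes an SD of 4 × 0.25 × 0.6 = 0.60 to baseline power against a residual SD of 0.5, so only 0.36/(0.36 + 0.25) = 59% of the baseline variance is speed. A walking baseline protects only as far as it also carries the participant's own deviation in power.

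**Step 4: the VIF check.** VIFs compare the listed regressors with one another, so an unlisted variable is invisible to them. With varying speed, step length's VIF was 1.3–1.7 in the tied-belt, resting-baseline runs of B. Step time and stance duration had VIFs of 14–42, because stance duration was assumed to follow step time closely; dropping one of those two leaves the other to pair with step length.

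**Step 5: common speed.** With tied belts, step length and step time are exactly collinear. With split belts, B gives VIFs of about 19 and 26 (both legs averaged) or 2 and 9.5 (one leg).

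**Step 6: cost per metre.** Under A it is (1 + 3v)/v = 3 + 1/v. One SD either side of 0.6 m/s at CV 30% is 0.42 and 0.78 m/s, giving 3 + 2.38 = 5.38 and 3 + 1.28 = 4.28. It still varies with speed, and AIC still kept step length in 52–78% of runs.

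**The case against.** The strongest reply is that the outcome wording speaks of reducing power, which most naturally means a PRE–POST change. At matched speed the artefact is then near chance. This stands: the large percentages require a level outcome, unequal speeds and a baseline that does not absorb speed, all together. The motor-adaptation section gives asymmetries as examples of its spatiotemporal parameters; if the regression uses the same form for step length and step time, the geometric argument does not apply to them. The regression section names bare length and time, so that reading is possible but not certain.

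Three stronger readings are tempting and should be resisted.
- A reader might infer that any reported gait association is merely speed. The documents do not support this, because the speeds, the outcome and the form of the regressors are all open.
- A reader might infer that at a common speed the list contains one variable twice. That is exact only for tied belts, whereas power is measured with split belts, and the planned VIF check partly covers the case.
- A reader might infer that the protocol never addresses belt speed. Part of the document was not available, so its absence can be asserted only for the regressor list.

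**Conclusion.** The concern holds conditionally. Belt speed is not in the list of regressors, the geometric link is sound, and neither VIF screening nor AIC guards against it. If speeds differed between participants, raw leg-averaged lengths and times were used, and the outcome is the level of net power, step length or step time is likely to be reported as associated with metabolic power because of speed alone. This is most marked with quiet standing as baseline power. With a reduction at matched speed or with asymmetry regressors, the artefact is small or absent. With a walking baseline it is small when PRE power tracks the participant's own POST power closely. Every percentage rests on assumed speeds, slopes and scatter; direction and rough size are informative, exact values are not. The point concerns interpretation of the association model; the AIH-versus-SHAM ANOVA does not use these regressors and is unaffected.

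**What to change.** - State whether belt speeds were common or individual and whether they were matched PRE to POST. Define the regression outcome (level or change), the form of the gait regressors, and baseline metabolic power.
- If speeds varied between participants, force mean belt speed from the treadmill settings into the metabolic regression, outside AIC selection and VIF screening, and list only one of mean step length and mean step time as a candidate. Adding speed while keeping both does not work cleanly: a VIF above 10 appeared in 100% of simulated runs.
- If speed was common to all, list only one of the two.
- Do not substitute cost per metre for the speed term, since it can still depend on speed.

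The cost is one covariate, a few sentences in the SAP and, as the text describes completed work, probably a re-run of one regression. Speed uses at most one degree of freedom. Six regressors and an intercept leave 26 − 7 = 19 residual degrees of freedom, and swapping speed for one of the gait pair leaves the same 19.
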